1. INTRODUCTION AND BACKGROUND

Osteoporosis has a devastating impact on quality of life of postmenopausal women, and is a significant cause of disability and morbidity. Numerous drugs are currently FDA-approved for the prevention and treatment of postmenopausal osteoporosis, the most frequent type of osteoporotic syndromes. However, most cases in the US remain untreated or ineffectively treated because of cost and/or adverse events of currently available drugs, leading to inadequate prescriptions of and poor compliance with anti-osteoporosis medications^{1,2}. For example, despite clear efficacy of bisphosphonate drugs in the secondary prevention of hip fracture, a recent large study in patients with hip fracture found that use of bisphosphonates decreased from an already dismal 15% in 2004 to an abysmal 3% in 2013³. These data underscore the critical need to identify inexpensive, safe and effective interventions for both the prevention and treatment of osteoporosis. Animal studies⁴⁻¹³ and a report in humans¹⁴ suggest that nutritional supplementation with probiotics may represent an effective, safe and inexpensive modality to prevent and treat osteoporosis. Studies from laboratories in the US and Europe have clearly shown that probiotics prevent the bone loss induced by ovariectomy (ovx)⁴⁻⁶. Adding to this evidence, we recently demonstrated that the probiotics *Lactobacillus rhamnosus* GG (LGG) and VSL#3 (containing 8 strains of live bacteria, namely *Bifidobacterium breve*, *B. longum*, *B. infantis*, *L. acidophilus*, *L. plantarum*, *L. paracasei*, *L. bulgaricus* and *Streptococcus thermophilus*) prevent ovariectomy (ovx)-induced bone loss by decreasing cytokine-driven bone resorption⁸. Furthermore, we showed that both LGG and VSL#3 induce bone anabolism in estrogen-replete mice.

2. OBJECTIVES AND STUDY PURPOSE

Based on the strong preclinical evidence from our laboratory and others, ***our primary hypothesis is that oral administration of VSL#3 is a feasible, well-tolerated and effective strategy to prevent bone loss in postmenopausal women.*** We further hypothesize that this simple approach will favorably impact biomarkers relevant to bone turnover, including inflammatory and osteoclastogenic cytokine production.

Specific Aim 1. To conduct a placebo-controlled, double blind, prospective clinical trial in which the commercially available oral probiotic VSL#3 will be administered to otherwise healthy, postmenopausal women for 12 months. The primary objective will be to demonstrate that VSL#3 administration safely maintains or improves bone density in the lumbar (L1-L4) spine, femoral neck, and total hip area in the study subjects at 1 year.

3. CRITERIA FOR PATIENT SELECTION

3.1 Inclusion criteria: 1) Willing and able to give written informed consent for participation in the study, 2) Age range 50-65 years, 3) Menopausal status (defined by >1 yr since last menstrual period or FSH level in the postmenopausal range), 4) Ambulatory, 5) Body mass Index (BMI) must be ≥ 18.0 and ≤ 32 kg/m² at screening, 6) Bone mineral density (BMD), expressed as T-scores, must be > -2.5 in the lumbar spine (L1-L4), the femoral neck, and the total hip, as measured by dual energy X-ray absorptiometry (DXA), 7) Commitment not to use any products that may influence the study outcome (see below), and 8) Ability to understand and comply with the requirements of the study.

3.2 Exclusion criteria: 1) Premenopausal status, 2) History of ≥ 1 previous atraumatic bone fractures after age 50; 3) Presence of established osteoporosis (T-score ≤ -2.5 , in the lumbar spine, femoral neck or total hip as measured by screening DXA), 4) History of immunological or bone-related disorders including: HIV infection, Type I diabetes mellitus, bone marrow or organ transplantation; Inflammatory bowel disease (ulcerative colitis, Crohn's disease); multiple myeloma; osteomalacia; osteosarcoma; Paget's disease; rheumatoid arthritis; systemic lupus erythematosus; parathyroid disorders, 5) uncontrolled type II diabetes mellitus (HgbA1c $\geq 7\%$ within the last 12 months), 6) History of bariatric surgery or other forms of malabsorption (including documented celiac disease, or chronic diarrhea), 7) Alcohol abuse, 8) Clinically significant chronic kidney disease (stage ≥ 2 , with total serum creatinine level > 2.5 mg/dL and calculated glomerular filtration rate (GFR) < 60 mL/min by the Modification of Diet in Renal Disease (MDRD equation), 9) Clinically significant cardiovascular disease (myocardial infarction, cerebral vascular accident or acute congestive heart failure within the previous 12 months, 10) Any malignancies, other than localized skin squamous cell carcinoma, diagnosed within the previous 5 years, or any history of metastatic cancer, 11) History of use of oral supplement products containing probiotic bacteria (more than once per week) within four weeks prior to

Version 10/17/18

baseline, 12) Current use (within the past 8 weeks) of any medication with known influences on the immune or skeletal system (e.g. immune modulation therapy, systemic glucocorticoids, systemic steroid hormones, 13) Use of oral or injectable bisphosphonates for more than 1 year within the last 5 years, 14) Current or past use (within 1 year) of Denosumab, Teriparatide, Raloxifene, hormone replacement therapy (HRT), calcitonin, or any other anti-resorptive agent other than bisphosphonates used for the prevention and treatment of osteoporosis, 15) Use of antibiotics during the previous two months or frequent user of antibiotics (>2 courses during the previous 12 months) for any cause, 16) Smoking or use of nicotine-containing products during the last six months, 17) Known hypersensitivity to any of the ingredients in the VSL#3 or the placebo study drug, 18) serum or plasma 25-hydroxyvitamin D [25(OH)D] concentration < 12 ng/mL, 19) uncontrolled thyroid disease (abnormal blood TSH level within the last 12 months and/or changing dose of thyroid replacement therapy within the last 12 months).

3.3. Number of patients to be studied: We propose to study a total of 40 patients. A total of 20 subjects will receive a placebo (control, 2 placebo sachets/day in a single dose), and 20 subjects will receive VSL#3 (2 sachets a day in a single dose).

3.4. Subject recruitment plan: We will employ several methods for identifying potentially eligible participants:

- a) We will post approved flyers throughout Emory-affiliated hospitals and clinics, Emory University and the surrounding Atlanta metropolitan area.
- b) We will utilize the study subject recruitment resources of the NIH-funded Atlanta Clinical and Translational Science Institute (ACTSI), including its weekly list-serve, clinical trial websites of Emory HealthCare, and ResearchMatch.org.
- c) Subjects will also be recruited among participants in an existing cohort of Emory University and Emory Healthcare employees, the Emory/Georgia Tech Predictive Health Initiative (PHI) Cohort, who have consented to be contacted for potential study participation in future research and who meet initial screening criteria based on the most recent data available (within previous 12 months)¹⁵.
- d) Participants may also be recruited by advertising (via flyers or in person) at health fairs and other Atlanta community events.
- e) We will approach potentially eligible subjects among patients seen in Emory HealthCare-affiliated Endocrinology, Obstetrics/Gynecology, Rheumatology and General Medicine clinics in Atlanta, GA. This will involve a prescreen of the electronic medical record facilitated by a partial HIPAA waiver for screening purposes. We will also identify potentially eligible subjects among patients who have undergone a recent bone density scan at Emory clinics and/or whose data is entered into the Emory BoneStation electronic record.
- f) Through the Emory Data Warehouse, we will receive a list of patients in the Emory system who meet eligibility criteria and who have agreed to be contacted about research studies either by phone or through a letter.
- g) Individual participating Emory clinics will generate a list of clinic patients who meet eligibility criteria and will send a letter (directly or through the study team) to potentially eligible patients describing the study and providing study contact information.
- h) A combination of the above three (e-g) strategies may be used, but the research team will only approach potential study participants in person (during clinic visits) or by letter unless there is available documentation that a potential participant is agreeable to being contacted by phone.

[figure not shown]
3.5 Study withdrawal: Participants may withdraw from the study at any time. Automatic withdrawal occurs when a participant refuses or is unable to take study drug, or refuses or is unable to complete study procedures, including the return visits to the Clinical Research Center at 6 and 12 months and the twice monthly study-related telephone calls required to ensure tolerance/compliance with the VSL#3 and placebo.

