Study drug tolerance will be assessed by obtaining serial measures of the Gastrointestinal Symptom Rating Scale (GSRS) every two weeks during the 12-month placebo or probiotic regimen²¹. These will be obtained with in-person interviews at the baseline and month 6 and 12 visits and by telephone contact with all subjects by the study coordinator every 2 weeks. Data will be analyzed within the 5 symptom domains depicting symptoms related to gastric reflux, abdominal pain, indigestion, diarrhea, and constipation. A GSRS total score, the sum of all 5 domains, will also be assessed. To our knowledge there is no published absolute or change in the GSRS score that is demonstrative of intolerance to a study drug or other treatment²¹⁻²³. Therefore we will *a priori* define intolerance to the study drug as a 50% increase in the total GSRS score from baseline at any two consecutive time points, or the new onset of a GSRS classifier score of 2 or 3 in at least three of the 15 gastrointestinal symptoms queried. If either of these signs of intolerance occurs, we will offer the subject the options of: 1) discontinuing from the study; 2) discontinuing the study drug but participating in the serial assessments (e.g. blood draws, DXA) in the research center, or 3) decreasing the dose of blinded study drug to one sachet/daily, with the option of resuming the two sachet/day study regimen upon resolution of symptoms. If intolerance symptoms recur, the same strategy will be followed. All episodes of intolerance to study drug and the twice-monthly GSRS data will be recorded by the study coordinator in the individual subject case report forms (CRFs) (see below).

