Valid reasons a patient can be off study include withdrawal of consent at any time during the study or the achievement of all required efficacy and safety end point information. Withdrawal of consent will be used only when the patient no longer wishes to participate in the trial and no longer authorizes the investigators to make efforts to continue to obtain their outcome data. Valid reasons for non-adherence to treatment include an inability to tolerate the intervention, toxicity, physician choice or need for other therapies. All patients will continue to be followed with all scheduled outcome evaluations until the end of the study. This strategy will

allow a true all-inclusive, intent-to-treat design and analysis. Patients will not be labeled 'dropouts' but as 'temporarily inactive' and the patient will be welcomed back to the trial when possible. The designation of 'lost-to-follow-up' will be applied at the end of the trial to patients that remained inactive. Monthly reports will summarize recruitment and retention rates, treatment adherence rates, observed and expected data on attendance to routine clinical visits and the degree of completeness of data capture. The DCC will establish performance standards before the trial. These standards will be reviewed and revised as needed during the trial to enhance the quality of trial conduct.

7.5.5 Data Management Considerations: The DCC will establish processes and work-flow to create and maintain a high quality research database for the trial while preserving the confidentiality of all subjects' data. It is difficult to implement a statistical analysis plan unless a data management plan has been followed to assure data quality and procedural adherence. Quality control will be applied to each phase of data handling to ensure that all data are reliable and have been processed correctly.

7.5.5.1 Case Report Forms (CRFs): The clinical investigators and the DCC will collaborate on the design of CRFs for each study. All CRFs will be designed using Adobe InDesign. Forms questions and lay-out will be optimized for ease of forms completion and ease of data entry.

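### Section 3.5 withdraws women who stop study drug, whereas 7.5.4 keeps them in outcome follow-up; on its ordinary reading 3.5 gives up their only post-baseline BMD and can bias the intent-to-treat comparison

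*Combined protocol and SAP*

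**What the plan says.** Three places in the combined protocol and SAP govern a woman who stops study drug.

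- **Section 3.5, Study withdrawal.** "Automatic withdrawal occurs when a participant refuses or is unable to take study drug, or refuses or is unable to complete study procedures". The procedures are spelled out as "including the return visits to the Clinical Research Center at 6 and 12 months and the twice monthly study-related telephone calls".
- **Section 7.5.4, on the intent-to-treat design.** "Valid reasons for non-adherence to treatment include an inability to tolerate the intervention, toxicity, physician choice or need for other therapies". On leaving the study: "Valid reasons a patient can be off study include withdrawal of consent at any time during the study", the other named reason being that all required end point information has been obtained. Withdrawal of consent is kept for a woman who no longer wishes to take part and "no longer authorizes the investigators to make efforts to continue to obtain their outcome data". The rule for everyone else is: "All patients will continue to be followed with all scheduled outcome evaluations until the end of the study".
- **Tolerance text after 4.10.** Once intolerance as defined on the GSRS occurs, "If either of these signs of intolerance occurs, we will offer the subject the options of" three courses. The first two are "discontinuing from the study; 2) discontinuing the study drug but participating in the serial assessments", with DXA given as an example of those assessments. The third is a reduced dose.

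The primary endpoint (4.1, 4.9) is change in L1-L4 BMD over one year. Table 1 and section 8 place DXA at screening or entry and at month 12, with none at month 6. Section 4.14 plans a repeated-measures mixed model that is valid if data are missing at random.

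**The concern.** A woman who cannot tolerate the product is withdrawn automatically under 3.5, is followed to the end under 7.5.4, and may choose to stay in for assessments under the tolerance text. Staff cannot apply all three, and nothing says which prevails.

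The choice matters because there is one post-baseline scan. If withdrawal under 3.5 ends follow-up, a woman who stops the product in month 3, or who refuses or cannot complete the calls or the month-6 visit, loses her 12-month BMD even though she might have attended. That loss depends on tolerance and adherence after randomisation, so the women left in each arm need no longer be comparable. With no intermediate BMD, nothing observed after randomisation tells the model how her bone density changed. Section 7.5.4 itself calls retention key to the intention-to-treat analysis, and 3.5 works against that.

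**Working it through.** **The rules side by side**

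| Situation | 3.5 | 7.5.4 | Tolerance text after 4.10 |
|---|---|---|---|
| Unable to tolerate the product | Automatic withdrawal | Non-adherence; outcomes continue | Woman chooses; one option keeps DXA |
| Refuses the product without GSRS-defined intolerance | Automatic withdrawal | Followed unless she withdraws consent | Not covered |
| Refuses or cannot complete calls or month-6 visit | Automatic withdrawal | Followed unless she withdraws consent | Not covered |
| Refuses the 12-month visit | Automatic withdrawal | BMD lost anyway | BMD lost anyway |

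The avoidable loss is in the first three rows.

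**The plan's own figure.** Section 4.13 gives n = 20 per arm, a difference of 0.03 g/cm² and SD 0.03 g/cm², with a two-sided 5% t-test. The standard error (SE) of the difference is 0.03 × √(2/20) = 0.0095, so the noncentrality is 0.03/0.0095 = 3.16 on 38 df. Power is 86.9%, which agrees with the stated figure of more than 85%. That calculation uses all 20 per arm. If 10% or 20% of each arm lacked the 12-month scan (assumed rates), power would be 83.0% (18 per arm) or 78.1% (16 per arm).

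**Illustration of bias.** The documents give no stopping rate and no figure for BMD after stopping, so both are assumed. Let w be the share of an arm withdrawn and g the retained women's mean change minus the withdrawn women's mean change. The mean of the arm as randomised is the retained mean − w × g. The retained comparison therefore exceeds the effect of assignment by

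gap = w(VSL#3) × g(VSL#3) − w(placebo) × g(placebo).

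*Case 1: only VSL#3 women stop.* The planned 0.03 benefit is real, and those who stop lose a fraction r of it. The effect of assignment is 0.03 × (1 − w × r), against 0.030 in retained women.

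| r | w = 10% (2 of 20) | w = 20% (4 of 20) |
|---|---|---|
| 1 | 0.0270 | 0.0240 |
| 0.5 | 0.0285 | 0.0270 |
| 0.25 | 0.02925 | 0.0285 |
| 0 | 0.0300 | 0.0300 |

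The full-reversion gaps are 0.003 and 0.006. Section 4.13 also states an SD of change of 0.02, for which the SE is 0.02 × √(2/20) = 0.0063.

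| SD | Gap/SE, 20 v 20 | Gap/SE at the reduced size (18 v 20; 16 v 20) |
|---|---|---|
| 0.03 | 0.32; 0.63 | 0.31; 0.60 |
| 0.02 | 0.47; 0.95 | 0.46; 0.89 |

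*Case 2: both arms lose women whose change is 0.015 worse than in those retained.* Losses of 20% v 20% (VSL#3 v placebo) give 0.20 × 0.015 − 0.20 × 0.015 = 0. Losses of 20% v 10% give +0.0015, and 10% v 20% give −0.0015. The sign depends on which arm loses more.

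**Does keeping her baseline in the model help?** The 4.14 type of model (arm-by-time means, compound-symmetric covariance, maximum likelihood) was simulated with 4,000 replicates, baseline mean 1.108, between-woman SD 0.15 (assumed), SD of change 0.03, and full reversion. With stoppers giving baseline only, it estimated 0.0301 (10%) and 0.0299 (20%), Monte Carlo SE 0.00016. With everyone followed it gave 0.0270 and 0.0239. The model returns the effect in retained women.

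**The case against.** The strongest reply is that 3.5 is one sentence and never says outcome collection ends, while 7.5.4 and the tolerance text both point towards a continued DXA. Section 7.5.4 also plans education at consent about the value of data after stopping the intervention and labels such women temporarily inactive. Section 7.5.3 leaves the definition of dropout to performance standards that are not in these documents. This is fair, and it makes loss of the scan an inference. But study withdrawal is ordinarily read as the end of follow-up, and the tolerance text itself separates leaving the study from stopping the product. The conflict remains.

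The second reply is that the size rests on assumptions. That also stands. Section 7.1 reports few side effects, and full reversion is the extreme case, since a woman who stops late would hardly lose a full year's benefit.

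Some stronger readings are not supported:

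- A reader might infer that one missed call or visit triggers withdrawal. Section 3.5 requires refusal or inability. For the same reason, the logging of missed contacts in the retention text before 4.13 is not a further contradiction.
- A reader might infer that nothing covers outcome follow-up when the investigator and Safety Officer stop the product under 7.3. Section 7.5.4 covers it, through toxicity and physician choice.
- A reader might see a gap for the woman who chooses to leave the study after intolerance. She has just been offered the option of keeping her assessments, so a second request is a matter of preference.

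**Conclusion.** The contradiction is certain and in current text. The consequence is conditional: if 3.5 is applied on its ordinary reading, women who stop the product, or who refuse or cannot complete the calls or the month-6 visit, lose a primary outcome that could have been obtained. The missing-at-random model would then have only baseline BMD and covariates for them.

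This can bias the intent-to-treat comparison. It would go too far to say that the result will be biased, or biased in favour of VSL#3. The gap stays below one standard error in every case shown and can take either sign. It is zero without reversion and, by the reversion mechanism, zero if VSL#3 has no effect. Women who miss some doses or take a reduced dose and stay in are unaffected. The point should be fixed because a scan not taken cannot be recovered at analysis; it is not fatal to the trial.

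**What to change.** Reconcile 3.5 with 7.5.4 and the tolerance text so that one rule governs outcome collection:

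1. Record stopping study drug, or failing to complete the calls or the month-6 visit, as non-adherence or missed contact. Neither should end outcome collection.
2. End outcome collection only on withdrawal of consent as 7.5.4 already defines it, or when collection is impossible.
3. Seek the scheduled 12-month DXA from every other randomised woman and analyse her in the arm to which she was randomised.

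The cost is a protocol wording change, mainly to the sentence in 3.5, with a check that the consent form and CRFs agree. Table 1 already schedules the 12-month visit and scan, so none is added. No rule on when study drug is stopped or reduced is changed.

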4. STUDY DESIGN AND METHODS

4.1 Overview of the study: This will be a 12-month, double-blind, randomized, placebo-controlled trial of VSL#3 or placebo (**Figure 1**). Participants will be randomized to the placebo group or the VSL#3 group and treated and followed serially for 12 months. Baseline and follow-up assessments will be performed during an outpatient visit in the Emory University Hospital (EUH) Clinical Research Network (CRN) site of the Atlanta Clinical and Translational Science Institute (ACTSI) before initiation of the study drug (entry), and 6, and 12 months following baseline assessments. Subjects will report to the CRN after having fasted for at least 8 hours.

Figure 1: Study schema for protocol “Use of a Commercially Available Combination Probiotic, VSL#3, for Bone Health in Postmenopausal Women”

The study will be conducted in a population of ambulatory, postmenopausal women aged 50-65 (BMI >18.5 and $\leq 30 \text{ kg/m}^2$), with a lumbar spine (L1-L4), femoral neck, and total hip BMD T-score > -2.5, as measured by DXA (see section 3 above). Women with osteoporosis (T score ≤ -2.5) will not be included in the study because at this stage of knowledge we find it unethical not to offer effective treatment to these individuals. We will recruit subjects of all ethnic groups. Covariates known to influence bone mass, including body mass index (BMI), history of smoking > 6 months prior to entry, alcohol use, baseline BMD of the lumbar spine, femoral neck and total hip area, bone fracture history and co-morbidities will be collected and controlled for in the final analysis. The primary endpoint is the change in bone mineral density (BMD) at the L1-4 lumbar spine over one year of study. Changes in BMD at the femoral neck and total hip area will be secondary endpoints. All BMD data will also be used as a tool for future studies power calculation and design. Additional endpoints will include changes in bone turnover markers and inflammatory/osteoclastogenic cytokines. These indices will provide much needed mechanistic information. To determine additional potential mechanisms of action of probiotics on health, we will conduct serial metabolomics analyses in the plasma, as well as serial assessment of plasma thiol/disulfide redox balance. The data will allow us to establish whether VSL#3 prevents bone loss and/or increases bone mass by regulating bone resorption, formation, or both. Based on our own data in mice following ovx, we hypothesize that treatment with VSL#3 will quickly decrease bone resorption and then stimulate bone formation, resulting in improved net BMD at least one site over the 12-month period of study.

4.2. Screening for eligibility: For study subjects identified among patients seen at the Emory-affiliated Endocrinology, Ob/Gyn, Rheumatology and General Medicine clinics, patients will be pre-screened for eligibility using the Emory Healthcare electronic medical record, and potentially eligible subjects will be approached during their clinic visit by a study coordinator or they will be contacted by phone or letter (as described above) to conduct a full screen. For potential study subjects identified outside of Emory-affiliated Clinics, potential subjects will contact the study team by phone and undergo a pre-screening discussion.

A full screen will consist of any screening medical/surgical and medication use information, blood and urine tests, screening DXA scan, and a physical examination. These may occur in the Emory-affiliated clinics by study personnel and/or in the Emory University Hospital CRN. Informed consent will be obtained prior to any research procedures. A verbal informed consent will be obtained from potential participants being pre-screened by phone prior to collecting information regarding eligibility criteria. In order to reach our goal of 40 randomized participants, up to 100 women may undergo a screening visit.

4.3 Informed consent process: A written and signed informed consent will be obtained in person in a private area. After identification of a person as potentially eligible for the study, approved study personnel will explain the study in detail in the consent form as well as verbally. Potential participants will be informed of the purpose of the study, the study protocol, and the routine and potential risks associated with the study procedures. All risks, costs, and benefits will be discussed. Participants will be assured of their right to withdraw at any time without prejudice to their care. They will be assured of confidentiality in maintaining records and reporting of results. Participants will have the option to provide permission to store biological samples for future studies. Any additional information regarding questions or concerns from potential or confirmed study participants will be provided.

We will request a partial HIPAA waiver to be able to access the medical record for screening.

For subjects recruited in Emory Clinics, the consent process will take place during a patient's clinic visit. Potential study participants will have the option of taking the blank, unsigned consent forms home to consider prior to signing the consent forms, in which case patients who decide to participate will complete a verbal consent by telephone and will complete the full, written consent process during their first study visit (prior to any procedures). For subjects recruited outside of Emory clinics, the consent process will take place during their EUH CRN screening visit. Participants will have ample time to call the study team with questions/concerns and make an informed decision about their participation in the study.

An Institutional Review Board (IRB) approved study designee will provide verbal and written consent. The study is discussed thoroughly with each potential participant, and she will be encouraged to ask questions regarding the study and her participation. If the potential participant decides to enroll, she will sign the written informed consent, as will the study team member conducting informed consent. A copy of the signed consent form will be provided to enrolled study participants. Subjects must be able to read, write and understand the consent documents. Study personnel will subjectively assess the capacity to give informed consent through the use of questions to ensure understanding and comprehension of the study. Only adults will participate.

4.4. Study Initiation and baseline assessments: Following screening and informed consent, baseline assessment and laboratory evaluation will be performed as outlined in **Table 1**. Dietary calcium and vitamin D intake will be reviewed by a registered dietitian. For participants not meeting at least the Recommended Dietary Allowance (RDA) for calcium (1200 mg) and vitamin D (600 IU), a recommendation will be provided for sufficient over-the-counter calcium citrate and/or vitamin D3 to meet the RDA. Participants will be allowed to continue their current regimens; however, they will be asked not to begin any new supplement, medical, or exercise therapies that could influence bone health. For individuals with a screening 25(OH)D < 20, a study physician will communicate with the participant's primary MD (and/or the participant directly) and recommend a standardized dose of vitamin D replacement (daily vitamin D₃ dose of 5,000 IU daily + 50,000 IU weekly for 12 weeks with a recheck of 25(OH)D level in 3-4 months).

Table 1. Study Endpoints by Visit

Assessments	Screen in clinic or CRN unit	Entry visit in CRN unit (max 4 weeks after screen visit)	6 mo visit in CRN unit (+/- 1 month)	12 mo visit in CRN Unit (+/- 1 month)
Medical/Surgical history, medication use, dietary calcium intake, alcohol intake, physical activity	x		x	x
Serum FSH (if indicated)	x			
Physical Exam	x		x	x
Concomitant medications	x	x	x	x
Gastrointestinal Symptom Rating Scale (GSRS)		Determine GCRS every 2 weeks 		
Study drug adherence assessment		Determine adherence every 2 weeks 		
Fasting serum markers of bone turnover (CTX and PINP)		x	x	x
Serum RANKL (free), OPG, TNF, IL-17		x	x	x
DXA scan: (lumbar spine, femoral neck, and total hip, total and regional body fat, total and regional lean body mass, visceral fat)*	x	x		x
Dietary Intake 3-day food record		x	x	x
BioElectrical Impedance Analysis (BIA) Body composition and total body water		x	x	x
Anthropometrics (height, weight, BMI, waist & hip circumference)				
Handgrip strength Hand-held dynamometer		x	x	x
Serum 25(OH)D	x			x
Stool microbiota composition		Xx	Xx	Xx
Plasma metabolomics		x	x	x
Plasma Amino thiols (GSH, GSSG, Cys, CySS)		x	x	x
Serum Intact PTH	x			
Complete blood count (CBC)	x		x	x
Chemistry profile	x		x	x
Urinalysis	x		x	x

*Note: First DXA scan will be done at the screening visit or the entry visit (not both).

4.5 Intervention: A total of 40 matched postmenopausal women meeting all specific inclusion/exclusion criteria will be blindly randomized to one of two study arms. **Arm A** (n=20): VSL#3 two active sachets [containing 450x10⁹ colony-forming units (CFU)/sachet], taken daily in a single administration; **Arm B** (n=20; control): two placebo sachets taken daily in a single administration. Thus, Arm A will receive 900 billion CFU daily and the control group (Arm B) will receive no supplemental probiotics (**Figure 1**).

4.6. Randomization and Stratification: Personnel in the Department of Biostatistics and Bioinformatics at Emory University have developed a centralized electronic randomization system that has been successfully used in several clinical studies¹⁶⁻¹⁹. Subjects will be blindly assigned in equal proportions, stratified by age (above and below 58 years) using a pseudo-random-number generator with randomly permuted blocks. These assignments will be stored in a backend database table within the iDataFAX database management system. This method serves to balance the treatment group assignments over the course of the study to ensure that the desired number of subjects will be allocated to each of the treatment groups at any time point during the randomization period. Permuted block sizes will not be disclosed to the blinded study personnel to minimize the likelihood of their being able to predict the next randomization assignment in the series. Briefly, after obtaining informed consent, all eligibility confirmation data will be entered into the web-based data management system by a research coordinator. If the patient meets all eligibility criteria, computer randomization will be performed and the coordinator will be provided with an audit trail of the process including a verifiable link between the unique study ID and treatment assignment. The application will be password protected with access restricted to designated personnel, including the EUH Investigational Drug Pharmacy staff pharmacist who **will dispense blinded study drug for subjects randomized to Arms A or B.**

4.7. Screening, Entry and Follow-up Evaluations: These will occur as outlined in Table 1. Adverse effects and safety data will be reviewed at least every 6 months by a Data Safety Officer, a gastroenterologist senior Emory faculty member with expertise in clinical trials who is unaffiliated with the study, as described below (Section 7.5).

4.8. Procedures to be performed (all for research purposes only):

- **Medical examination:** Medical history and medications will be reviewed by a member of the research team, and a physical exam will be completed by a licensed physician, as required by the clinical research unit. Habitual alcohol intake and dietary calcium intake (based on reported supplements, dairy, and other high-calcium foods) will be assessed.
- **Urine collection:** Urine will be collected for standard urinalysis indexes.
- **Anthropometric measurements:** Height and weight will be measured without shoes. Height will be measured with a manual stadiometer. Weight will be measured with a digital scale. Body mass index (BMI) will be calculated from height and weight. Waist and hip circumference will be measured with a flexible measuring tape.
- **Blood sampling:** Up to approximately 70 mL of fasted blood will be collected at every visit from a peripheral vein. Blood will be drawn for determination of plasma and serum biomarkers, plasma metabolomics, plasma redox markers, and standard clinical blood tests listed in **Table 1** above. Blood will also be stored for use for future studies, with consent from the study participant.
- **Stool collection:** Study subjects will be provided with a kit containing detailed instructions for stool collection and shipping. The kit contains a stool sample shipping tube, an adhesive paper for stool collection, a spatula for placing a small amount of stool into the tube, a biosafety bag and a pre-paid FedEx envelope for shipping the stool sample directly to the study lab within 48 hours.
- **Bone density analysis:** DXA will be used to measure bone density of the spine (L1-L4 segment) and the hip (non-dominant femoral neck and total hip area). Participants will be asked to lie still on a scanning table with their arms at their sides for approximately 20 minutes. All DXA scans will be performed on the same device within the Emory CRN by an experienced technician using a GE Lunar iDXA machine. Areas of interest will include the lumbar spine (L1-4), the femoral neck and the total hip). DEXA will also provide information about total and regional body fat, lean body mass.
- **Three-day food records:** Participants will be asked to complete a food diary for three days (2 weekdays and 1 weekend day) where they will record everything they eat and drink, including supplements. They will be given food records prior to their study visit and asked to return completed food records on the day of their visit. Alternatively, participants may choose to email or mail study investigators the completed food record.
- **Body composition analysis:** In addition to DEXA, body composition may also be assessed using bioelectrical impedance analysis (BIA); for this procedure participants will lie still on a table for <5 minutes with electrodes placed on hands and feet.

- **Handgrip strength:** A small, handheld dynamometer will be used to measure grip strength. Participants will be asked to squeeze the instrument as hard as they can for 3 seconds, which will measure the pounds of force applied.
- **Questionnaires:** Participants will be asked to answer a standardized, validated questionnaire (15 questions) about GI symptoms segregated into 5 symptom domains (see below). They will also complete a questionnaire assessing their habitual physical activity (Modified Baecke Questionnaire)²⁰.

4.9. Primary Endpoint: The **primary endpoint is** change in BMD of the lumbar spine (L1-L4 segment), as measured by DXA.

4.10 Secondary Endpoints (please see Table 1 above): Serial measures of: 1) bone density of the non-dominant hip (femoral neck and total hip area) as measured by DXA, 2) serum collagen type 1 cross-linked C-telopeptide (CTX) concentrations (a marker of bone resorption), 3) serum procollagen type I N propeptide (PINP) concentrations (a marker of bone formation), 4) serum free receptor activator of nuclear factor kappa-B ligand (RANKL) concentrations, 5) serum osteoprotegrin (OPG) concentrations, 6) serum tumor necrosis factor- α (TNF α), 7) serum interleukin-17 (IL-17) concentrations, 7) total and regional body fat (including visceral fat) and lean body mass as measured by DXA and BIA, 8) plasma thio/disulfide redox biomarkers, 9) compliance with study drug administration 10) overall study recruitment and retention, and 11)) **stool microbiota composition**. Measurements of indices of bone turnover and cytokine levels will provide much needed mechanistic information to establish whether VSL#3 may prevent bone loss and/or increases bone mass by regulating bone resorption, formation, or both. Based on animal data, we hypothesize that treatment with VSL#3 will quickly decrease bone resorption and then stimulate bone formation.

